7 DEVICE APPLICATION

7.1 Study Devices

RHA® [REDACTED] with [REDACTED]: A sterile, biodegradable, biocompatible, viscoelastic, clear, colorless, homogenized gel implant. It consists of cross-linked hyaluronic acid produced by fermentation of *Streptococcus zooepidemicus*, formulated to a concentration of 15 mg/g and 0.3% w/w [REDACTED] in a physiologic buffer [REDACTED]

RHA® [REDACTED] with lidocaine: A sterile, biodegradable, biocompatible, viscoelastic, clear, colorless, homogenized gel implant. It consists of cross-linked hyaluronic acid produced by fermentation of *Streptococcus zooepidemicus*, formulated to a concentration of 15 mg/g and 0.3% w/w lidocaine in a physiologic buffer [REDACTED]

For additional information regarding RHA [REDACTED], please refer to [REDACTED] Investigator's Brochure.

7.2 Injection of Study Devices

At Visit 1, each enrolled and randomized subject will receive injections of RHA® [REDACTED] with [REDACTED] into the perioral rhytids of the upper left quadrant or the upper right quadrant, and injections of the control device (i.e., RHA® [REDACTED] with lidocaine) into the contralateral upper quadrant. Using the same device as the upper quadrant for that side, the lower perioral quadrant of a side will be injected only after both upper perioral quadrants have been injected and only if needed.

7.2.1 Injection Depth

7.2.2 Injection Technique

The injection technique (e.g., linear threading, cross hatching, fan like administration, multiple puncture, etc.) will be at the discretion of the TI, and will be recorded. The same injection technique will be used on both sides of the mouth. [REDACTED]

For the purposes of this study, the lip will be defined as the structures within the vermilion border. The focus of this study is to treat perioral rhytids, and there will be no augmentation of the lips, but the vermilion border may be treated to ensure a satisfactory result of the treatment of the perioral rhytids.

Devices will be injected using the needle that is provided within the standard packaging of the device; the TI is not permitted to use a needle of different gauge or length.

7.2.3 Supplementary Anesthesia

Both study devices contain an anesthetic. Additional anesthesia is prohibited (e.g., EMLA, dental blocks, ice, etc.). Ice may be used at the discretion of the TI for post-injection treatment for pain or discomfort, but only after all injection pain assessments for both sides of the mouth have been

[REDACTED]

completed (i.e., at 60 minutes post-injection).

[REDACTED]

[REDACTED]

[REDACTED]

[REDACTED]

[REDACTED]

[REDACTED]

- The CAUTION statement mentioned above

The Investigator Brochure will provide all relevant contraindications, hazards, adverse effects, warnings and precautions.

The study device is to be stored at room temperature (2°C to 25°C) in a secure restricted area.

7.3.1 Relabeling

Real-time aging testing is in progress for the study devices. As new test data will become available throughout the course of the study, the shelf life of the study devices may be extended through the course of the study. The site monitor and/or study coordinator will be responsible for relabeling the Tyvek lid with the new expiry date. The site monitor and/or study coordinator will follow a specific procedure to perform and verify the product relabeling with the extended expiry date (to be provided in a separate guidance document). The relabeling process will be documented. The study devices may also be returned to the Sponsor to be relabeled. When the study devices have reached the expiry date as indicated on its label, the TI should segregate them and follow the instructions from the site monitor as to relabeling by the site monitor and/or study coordinator or for returning the devices to the Sponsor.

It is the responsibility of the TI to verify that a device is within its expiry date before being used. The initial shelf life of the study devices will be approximately 9 months; however, as devices being subjected to real time aging are being tested periodically, the shelf-life could be extended.

7.4 Study Device Supply and Accountability

The study Sponsor will ensure that participating sites are provided with a sufficient supply of study devices for all treatments. It is forbidden to use a study device for purposes other than defined in this protocol. Syringes are single use and must not be shared between subjects.

Study devices must be kept in a locked area with access restricted to designated study personnel. The Principal Investigator or designee will inventory and acknowledge receipt of all study device shipments, and ensure that the integrity of study devices is not jeopardized prior to use.

Accurate accountability records will be maintained that include batch numbers, quantities received/returned/destroyed, as well as dates and volumes administered, and the site monitor will be provided access to the study devices and records for periodic review.

Unused syringes will be returned to the Sponsor at the end of the study unless other arrangements are agreed upon in writing. **Used syringes** will be destroyed as per each site's standard procedures.

7.4.1 Other Study Supplies

Supplies that are unique to the study will be provided by  (e.g., UPTs, photographic equipment, paper study diaries, source document worksheets, etc.). The site is responsible for routine supplies related to pre-/post-injection care (e.g., alcohol wipes, gauze, etc.).

7.5 Concomitant Medications and Procedures

Any medication or procedure, including over-the-counter preparations, that the subject takes during the study protocol period is considered concomitant medication and will be captured on the Concomitant Medications and Procedures page of the eCRF.

[REDACTED]

[REDACTED]

[REDACTED]

[REDACTED]

[REDACTED]

[REDACTED]

[REDACTED]

[REDACTED]

[REDACTED]

[REDACTED]

[REDACTED]

[REDACTED]

[REDACTED]

[REDACTED]

[REDACTED]

[REDACTED]

[REDACTED]

[REDACTED]

[REDACTED]

[REDACTED]

[REDACTED]

[REDACTED]

[REDACTED]

[REDACTED]

[REDACTED]

The decision to administer a prohibited medication/treatment is done with the safety of the study participant as the primary consideration. If the permissibility of a specific medication/treatment is in question, the Medical Monitor should be contacted before the prohibited medication/treatment is administered.

8 DATA COLLECTION

[figure not shown]
8.1 Electronic Case Report Form

Treatment and follow-up of subjects will be recorded in a 21 CFR part 11 compliant eCRF. Data will be first recorded into the medical record and study specific source document worksheets prior to entry into the eCRF. The study coordinator will refer to these worksheets in conjunction with the medical record in order to complete data entry into the eCRF.

In order to review and electronically sign the eCRF, the TI will have an individual login password that will allow them to view only the data that they have generated. The TI must ensure that they electronically sign for completed eCRFs on a timely basis.

8.2 Subject Diaries

Subjects will record Common Treatment Responses (CTRs) for 30 days post-injection using paper-based diaries. Data recorded in this diary will be entered into the eCRF by the study coordinator.

Subjects will also record “duration of anesthetic effect” using paper-based diaries. Data recorded in this diary will be entered into the eCRF by the study coordinator.

8.3 Photography

Calibrated photographs will be taken at Visit 1 (pre-injection and post-injection) and Visit 2 according to a standardized protocol incorporating appropriate quality control processes (i.e.,

9 STUDY EVALUATIONS

9.1 Informed Consent

The TI (or designate) will explain the benefits and risks of study participation to each subject. Written informed consent must be obtained prior to any study related procedure.

9.2 Visit Procedures

9.2.1 Visit 1 (Screening / Enrolment / Treatment)

Procedures that can be completed up to 14 days before V1 are indicated by “+”

- Written informed consent⁺
- UPT (if female subject of childbearing potential)⁺
- Inclusion / exclusion criteria⁺
- Medical history and demographics⁺
- Concomitant medications/treatments⁺

- Randomization to study treatment (i.e., left side, right side)
- Photography (pre-injection and post-injection)
- Injection of study devices
- TI Assessments

- Subject Assessments

- CTR Diary and “Duration of Anesthetic Effect” Diary
 - Dispense diaries to subject and train subject on proper completion
 - Train subjects in recognizing potentially rare events of injection into the vascular system (as described in the CTR diary), and to contact their doctor immediately if an event is suspected

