4 OVERVIEW OF STUDY DESIGN

4.1 Study Design

[figure not shown]
This is a randomized, controlled, double-blinded, within-subject (split-face), multicenter, prospective study to investigate whether RHA[®] [REDACTED] with [REDACTED] is non-inferior to RHA[®] [REDACTED] with lidocaine in terms of injection site pain felt by the subject during injection.

At screening, the Treating Investigator (TI) will evaluate subjects' perioral rhytid severity (using the Perioral Rhytid Severity Rating Scale; PR-SRS) to confirm eligibility and to establish a pre-treatment score for assessing aesthetic improvement.

At Visit 1, RHA[®] [REDACTED] with [REDACTED] will be administered in a random sequence (first or second injection) and side of the mouth and RHA[®] [REDACTED] with lidocaine will be administered to the other side. Study subjects and the TI injecting study devices will be blinded.

[figure not shown]
Immediately after injection of an upper perioral quadrant, subjects will rate injection site pain experienced **during injection** using a 100 mm Visual Analog Scale (VAS). Injection site pain in each side of the mouth will also be assessed at 15, 30, 45 and 60 minutes after the upper quadrant was injected.

Safety evaluation will consist of AE assessments, [REDACTED] [REDACTED] a 30-day CTR diary, and a follow-up call performed by the study site at 72 hours after injection.

Subjects will attend Visit 2 (30 days post-injection) during which efficacy and safety assessments will be conducted. Subjects who present with an unresolved clinically significant device related AE at Visit 2 will receive the optional follow-up phone call no later than 30 days after Visit 2. If the clinically significant AE remains unresolved, the Investigator will request that the subject attend the optional in-clinic follow-up visit (i.e., Visit 3) within 5 working days. Follow-up of the clinically significant AE will continue until the AE is resolved or the TI determines that additional follow-up is not necessary.

[figure not shown]

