5 STUDY POPULATION

5.1 Inclusion Criteria

1. Outpatient, male or female of any race, 22 years of age or older. Female subjects of childbearing potential must have a negative UPT at Visit 1 and practice a reliable method of contraception throughout the study.

[REDACTED]

[REDACTED]

[REDACTED]

[REDACTED]

[REDACTED]

2. Moderate to severe bilateral perioral rhytids (grade 2 or 3 on the four point PR-SRS).
3. Perioral rhytids of the same PR-SRS grade on the left and right sides of the mouth.

[REDACTED]

5. Able to follow study instructions and complete all required visits.
6. Sign the IRB-approved ICF, Photographic Release Form, the Authorization for Use and release of Health and Research Study Information (HIPAA) form, and if applicable the California Experimental Research Subject's Bill of Rights prior to any study-related procedures being performed.

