6 TREATMENT ALLOCATION, RANDOMIZATION AND BLINDING

All subjects who have signed an ICF will receive a 3-digit subject number, starting at 001. Subject numbers will be assigned in ascending order and will be coupled with the site identification number for unique identification of each subject. The subject number will be used to identify the subject throughout the study. Subjects withdrawn from the study will retain their subject number; new subjects will be allocated a new subject number.

Upon qualifying for treatment, subjects will be randomized for the side of mouth and the order of injection of study devices [REDACTED]. If needed to improve cosmetic results, the lower perioral quadrant of a side will be injected only after both upper perioral quadrants have been injected.

Subjects will be considered “enrolled” at the time of consent, and will be considered “enrolled and randomized” at the time of randomization. The required sample size is based on “enrolled and randomized” subjects. If an enrolled subject withdraws from the study prior to being randomized, he/she may be replaced.

This is a double-blinded study in which subjects and TIs will be blinded to treatment allocation.

Designated site personnel will secure the randomization/treatment allocation information and any other record of study treatment from potential discovery by the TI or the subject. Any instance where the blind is opened to the TI or subject will be documented in writing.

If it is medically imperative to know what device was injected into the left and right perioral rhytids, the TI or study coordinator will contact [REDACTED] to confirm the rationale for unblinding. If appropriate, [REDACTED] and/or the Sponsor will approve unblinding and treatment assignments for that particular subject will be disclosed. The rationale for breaking the code must be recorded in subjects’ medical record and eCRF.

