9.2.3 Visit 2 (30 days from V1; ±3 days)

- Concomitant medications/treatments
- Photography

- TI Assessments

[Redacted]

[Redacted]

- Subject Assessments

[Redacted]

- Collect and review CTR Diary and “Duration of Anesthetic Effect” Diary

- Next Study Visit

- *If Subject presents with an unresolved device related clinically significant AE, proceed to Follow-up Phone Call.*
- *If Subject does not present with an unresolved device related clinically significant AE, the subject will **exit** the study and optional treatment with a commercially available product approved for injection into the perioral rhytids will be offered to subjects with remaining lines and/or wrinkles in the no-treatment zone.*

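### Inclusion criterion 1 requires a negative pregnancy test at Visit 1, the injection day, but Protocol 9.2.1 lets the test and the eligibility check be done up to 14 days earlier (minor inconsistency)

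*Protocol*

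**What the plan says.** Inclusion criterion 1, worded alike in the Protocol synopsis and in section 5.1, sets the timing of the urine pregnancy test (UPT): "Female subjects of childbearing potential must have a negative UPT at Visit 1".

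Section 9.2.1, which lists the Visit 1 procedures, opens with an allowance: "Procedures that can be completed up to 14 days before V1 are indicated by" a plus sign. Among the lines that carry the sign are "UPT (if female subject of childbearing potential)" and "Inclusion / exclusion criteria". Randomization and injection do not carry it.

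Section 7.2 places treatment at the same visit: "At Visit 1, each enrolled and randomized subject will receive injections of" the study devices. Section 6 links eligibility to allocation: "Upon qualifying for treatment, subjects will be randomized for the side of mouth and the order of injection of study devices".

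Section 9.4.5 requires a negative test before the device is injected, but names neither a day nor a window.

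**The concern.** The criterion and the visit procedures give different timings for the same test. Criterion 1 ties it to Visit 1. The procedures list tells site staff that it may be done up to two weeks ahead, and that the eligibility check may be completed ahead as well. No visible line in 9.2.1 calls for a repeat test or a re-check of eligibility on the injection day.

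Two things are at stake. The first is safety: pregnancy is an exclusion, and a test that is two weeks old cannot rule out a pregnancy that has become detectable since. The second is compliance: a site that works from the procedures list could treat a subject who does not meet criterion 1 as worded, and would then have an eligibility deviation to report under section 13.3.

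**Working it through.** The check is a comparison of texts. No power, sample-size or error-rate calculation applies, and the plan gives no figure to reproduce.

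**Step 1: is Visit 1 the injection day?** Section 7.2 says that injections are given at Visit 1. The timing of Visit 2 confirms it. Section 4.1 says "Subjects will attend Visit 2 (30 days post-injection) during which efficacy and safety assessments will be conducted", and the heading of 9.2.3 reads "Visit 2 (30 days from V1; ±3 days)". The offset between Visit 1 and injection is 30 − 30 = 0 days.

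**Step 2: how old may the test be at injection?**

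| Source | Timing given | Permitted age of test at injection |
|---|---|---|
| Synopsis and 5.1, criterion 1 | At Visit 1 | 0 days |
| 9.2.1, UPT line with plus sign | As early as 14 days ahead of Visit 1 | 0 to 14 days |
| 9.4.5 | Before injection, no window | Not limited; fits both of the above |

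The largest difference between the two explicit timings is 14 − 0 = 14 days.

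**Step 3: does a test done 1 to 14 days before Visit 1, and not repeated, comply?** It complies with 9.2.1 and with 9.4.5. It does not comply with criterion 1 as worded.

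**Step 4: does a later step catch it?** The eligibility line in 9.2.1 carries the same plus sign, so a site may complete that check before Visit 1 too. Section 6 then randomizes a subject who has qualified. Nothing visible between qualification and injection requires the test again.

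**Step 5: how many subjects?** At most 30 subjects are treated. The documents give neither the number of women of childbearing potential nor the number who would be tested before Visit 1, so no estimate is possible.

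**The case against.** The strongest reply is that the two texts can be read together. Section 9.2.1 is headed as a combined screening, enrolment and treatment visit and lists the UPT under it. On that reading, criterion 1 names the visit and 9.2.1 supplies its window. This does not hold, because 9.2.1 itself places the marked procedures before Visit 1. In the protocol's own terms, an early test is not a test at Visit 1.

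A second reply is that criterion 1 is mandatory and the plus sign only permissive, so a site that applies the criterion literally still tests on the day. That is true and limits the harm. It does not remove the mismatch, since staff working from the procedures list are told that an earlier test is acceptable.

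A third is that the mark on the eligibility line need not mean that eligibility is closed early. Exclusion 10 looks back two weeks from Visit 1, so it cannot be fully judged at a check made before that visit. This is a fair point about intent, but no visible text in 9.2.1 asks for the re-check.

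A fourth is that criterion 1 could instead be reworded to accept a test within 14 days. That would also make the texts agree. However, same-day testing is the rule the protocol states twice, so the smaller change is to bring the procedures into line with it.

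The reservation that stands concerns hidden text. Lines after criterion 1 in 5.1 are redacted, and the schedule of activities to which the synopsis refers is not visible. Either may already require a same-day test, and the safety consequence would then largely fall away. The plus sign would still contradict that requirement.

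**Conclusion.** The inconsistency is real on the visible text, and it is minor. The permitted age of the test at injection is 0 days under criterion 1 and up to 14 days under 9.2.1, and 9.4.5 does not settle which applies. The pregnancy exclusion and the contraception requirement keep the residual risk low, and the number of women affected is unknown. The point has no bearing on the pain comparison or its analysis. It merits correction because it concerns subject safety and eligibility and is cheap to put right. Confidence is medium, because the redacted lines and the unseen schedule could already resolve the practical question.

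**What to change.** Leave criterion 1 as it is and remove the plus sign from the UPT line in 9.2.1. If an early screening test is useful to sites, keep it but add a repeat negative test on the day of injection, before randomization. In 9.4.5, state that the negative test is obtained on the injection day, before the device is given. If the redacted text or the schedule already requires a same-day test, only the plus sign and the 9.4.5 wording need to change.

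The cost is an edit to two sections and, at most, one extra urine test for each woman of childbearing potential screened before Visit 1.

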9.2.2 Follow-up Phone Call (72 hours post-injection)

- CTR diary review
- Anesthetic effect duration diary review
- Concomitant medications/treatments review
- AE review

9.2.3 Visit 2 (30 days from V1; ±3 days)

- Concomitant medications/treatments
- Photography

- TI Assessments

[Redacted]

[Redacted]

- Subject Assessments

[Redacted]

- Collect and review CTR Diary and “Duration of Anesthetic Effect” Diary

- Next Study Visit

- *If Subject presents with an unresolved device related clinically significant AE, proceed to Follow-up Phone Call.*
- *If Subject does not present with an unresolved device related clinically significant AE, the subject will **exit** the study and optional treatment with a commercially available product approved for injection into the perioral rhytids will be offered to subjects with remaining lines and/or wrinkles in the no-treatment zone.*

9.2.4 Follow-up Phone Call – Optional (no later than 30 days from V2)

- Concomitant medications/treatments review

- AE review

- *Confirm if subject is still experiencing the unresolved clinically significant device related AE(s)*
 - *If yes, the site will request that the subject attend the optional in-clinic within 5 working days.*
 - *If no, the subject will **exit** the study*

[Redacted]

[Redacted]

[Redacted]

[Redacted]

[Redacted]

[Redacted]

[Redacted]

[Redacted]

[Redacted]

[Redacted]

[Redacted]

[Redacted]

- Study Exit

9.3 Effectiveness Variables

9.3.1 Anesthetic Effectiveness Variables

[figure not shown]
9.3.1.1 Injection Site Pain - Primary Effectiveness Variable

[figure not shown]
[figure not shown]
[figure not shown]
Injection pain will be self-assessed by the subject using a Visual Analog Scale (VAS) Pain Scale Ruler (see Figure 3 below). The VAS Pain Scale Ruler has two sides. Using the side that shows faces and is labeled “Pain Assessment Tool”, subjects will move the slider to the location that represents their level of pain. The site will use the other side of the ruler to determine the VAS score (expressed in units of mm).

Figure 3. VAS Ruler

Immediately after injection of an upper perioral quadrant, subjects will rate injection site pain **during injection**. Injection site pain in each side of the mouth will also be assessed at 15, 30, 45 and 60 minutes after the upper quadrant for that side was injected.

The occurrence of injection site pain is not to be considered an AE unless it is in excess to that typically observed following injection of a dermal filler (as determined by the TI).

[REDACTED]

[REDACTED]

[REDACTED]

[REDACTED]

[REDACTED]	[REDACTED]	[REDACTED]	[REDACTED]	[REDACTED]
[REDACTED]	[REDACTED]	[REDACTED]	[REDACTED]	[REDACTED]
[REDACTED]	[REDACTED]	[REDACTED]	[REDACTED]	[REDACTED]
[REDACTED]	[REDACTED]	[REDACTED]	[REDACTED]	[REDACTED]
[REDACTED]	[REDACTED]	[REDACTED]	[REDACTED]	[REDACTED]
[REDACTED]	[REDACTED]	[REDACTED]	[REDACTED]	[REDACTED]

[REDACTED]

[REDACTED]

[REDACTED]

[REDACTED]	[REDACTED]
[REDACTED]	[REDACTED]
[REDACTED]	[REDACTED]
[REDACTED]	[REDACTED]

[REDACTED]

[REDACTED]

[REDACTED]

[REDACTED]	[REDACTED]
[REDACTED]	[REDACTED]
[REDACTED]	[REDACTED]
[REDACTED]	[REDACTED]

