
Anesthetic Effectiveness
	
 • Injection Site Pain during injection in the upper perioral quadrants (primary endpoint) • Injection Site Pain at 15, 30, 45 and 60 minutes post-injection in each side of the mouth

Evaluations	
[REDACTED]
Aesthetic Effectiveness Evaluations	
[REDACTED]
 
[REDACTED]
Safety Evaluations	
Adverse Events.Post-injection Common Treatment Response [REDACTED] (30-day patient CTR diary). 
[REDACTED]
 
[REDACTED]
Primary Endpoint	Injection site pain felt during injection of the upper perioral quadrant assessed by the subject immediately following injection with RHA® [REDACTED] with [REDACTED] compared to the injection site pain felt during injection into the contralateral upper perioral quadrant assessed immediately following injection with RHA® [REDACTED] with lidocaine.
Secondary Endpoints	
[REDACTED]
 
[REDACTED]
 
[REDACTED]
 
[REDACTED]
 
[REDACTED]
 
[REDACTED]
 
[REDACTED]
Sample Size	
[REDACTED]
 
[REDACTED] the Sponsor increased the sample size of the study [REDACTED] to 30.

Statistical Methods	
[REDACTED]
 
[REDACTED]
 
[REDACTED]

FIGURE 1. STUDY SCHEMATIC

[figure not shown]

TABLE OF CONTENTS

PROTOCOL APPROVAL SIGNATURE PAGE	2
INVESTIGATOR SIGNATURE PAGE	3
SYNOPSIS	4
TABLE OF CONTENTS	10
CONTACT LIST	13
ABBREVIATIONS	14
1 INTRODUCTION	15
1.1 Background	15
1.2 Rationale for Study	16
1.3 Hypothesis	16
2 STUDY OBJECTIVE	17
3 COMPLIANCE STATEMENT	18
3.1 Variations to the Protocol	18
3.2 Investigational Sites	18
3.3 Training and certification on the Perioral Rhytids Severity Rating Scale (PR-SRS)	18
3.4 Medical Monitor	19
3.5 Photography	19
4 OVERVIEW OF STUDY DESIGN	20
4.1 Study Design	20
4.2 Study Design Rationale	21
4.2.1 Study Population	21
4.2.2 Primary Endpoint	21
5 STUDY POPULATION	22
5.1 Inclusion Criteria	22
5.2 Exclusion Criteria	22
6 TREATMENT ALLOCATION, RANDOMIZATION AND BLINDING	24
7 DEVICE APPLICATION	25
7.1 Study Devices	25
7.2 Injection of Study Devices	25
7.2.1 Injection Depth	25
7.2.2 Injection Technique	25
7.2.3 Supplementary Anesthesia	25
7.2.4 [REDACTED]	[REDACTED]
7.3 Labeling, Packaging and Storage	27
7.3.1 Relabeling	28
7.4 Study Device Supply and Accountability	28
7.4.1 Other Study Supplies	28

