9.3.2.5 Treatment Volume

[figure not shown]
[REDACTED]

The total volume injected in each upper quadrant will be collected for each study device. Additionally, total volume required injected in each lower quadrant will be collected. Treatment volume will be measured to an accuracy of 0.1 mL.

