4.1.3 Injection Sequence

Upon qualifying for treatment, subjects will be randomized for the side of mouth and the order of injection (i.e., left or right / 1st or 2nd order). Both upper perioral rhytids will be injected prior to injection of either lower perioral rhytid. [REDACTED]

[REDACTED]

[REDACTED]

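### Could pain from an optional lower-quadrant injection contaminate the 15 to 60 minute side-of-mouth pain ratings?

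*Protocol*

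**What the plan says.** The primary rating concerns pain during injection of an upper quadrant and is given immediately after that quadrant is injected. The later ratings cover a wider area. Protocol 9.3.1.1 sets them out as follows: "each side of the mouth will also be assessed at 15, 30, 45 and 60 minutes after the upper quadrant for that side was injected". In the synopsis, the list of anesthetic effectiveness evaluations is shorter: "Injection Site Pain at 15, 30, 45 and 60 minutes post-injection in each side of the mouth". Protocol 4.1 and SAP 2.1 put the ratings "at 15, 30, 45 and 60 minutes after the upper quadrant was injected", without repeating which side is meant.

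The lower quadrant is optional. Protocol 6 states that "the lower perioral quadrant of a side will be injected only after both upper perioral quadrants have been injected", and SAP 4.1.3 agrees: "Both upper perioral rhytids will be injected prior to injection of either lower perioral rhytid". Protocol 7.2 fixes the product for a lower injection: "Using the same device as the upper quadrant for that side".

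Two other passages bear on the point. Protocol 7.2.3 allows ice after injection, but "only after all injection pain assessments for both sides of the mouth have been" completed, which it places at 60 minutes. Protocol 9.3.2.5 records lower-quadrant treatment by amount: "total volume required injected in each lower quadrant will be collected".

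**The concern.** The area rated is the whole side, but the clock starts with the upper quadrant alone. On the legible text, a lower injection may come at any time after the second upper quadrant, so it could fall before the 15-minute rating or between two later ones. A subject asked about that side would then be reporting two injections of different age. If only one side needed the lower injection, the left-right comparison would set a recently injected side against one injected earlier.

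The ice rule sharpens the doubt. The plan protects this hour from cooling, yet no legible sentence protects it from another needle on the same side. Volume shows which sides had a lower injection but not whether that came before a given rating, so affected ratings could not be picked out afterwards from volume alone. The clock is also worded in three ways.

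At stake are ratings that the synopsis lists as measures of anesthetic effectiveness, in a paired comparison of at most 30 subjects. Their meaning would be less clear and their differences noisier.

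**Working it through.** The plan gives no figure for this point, and the sample-size inputs are redacted, so there is nothing to reproduce. The check is a comparison of the texts, followed by an illustration of size.

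**1. Area rated.** The synopsis, Protocol 4.1, Protocol 9.3.1.1 and SAP 2.1 all give the side of the mouth as the area for the later ratings. The synopsis limits the primary rating to the upper quadrants in the line just before. The two areas are distinguished, and each is stated consistently.

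**2. Clock.** Protocol 9.3.1.1 is the operational section and ties time zero to the upper quadrant of the side being rated. Protocol 4.1 and SAP 2.1 speak of each side and then of the upper quadrant, which reads naturally as that side's own. The synopsis bullet is shorthand, and the synopsis design paragraph gives the upper-quadrant clock. The three wordings are compatible.

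**3. Primary endpoint.** Each primary rating follows its upper quadrant at once, and lower injections wait until both uppers have been injected. The primary score is therefore taken before any lower injection.

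**4. Direction.** A side gets the same device above and below, so its score never mixes the two products. Side and order are randomized, and subject and injector are blinded. Extra pain from a one-sided lower injection thus has no designed tendency to fall on either device.

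**5. Timing, if lower injections do come early.** Suppose the lower quadrant is injected L minutes after that side's upper quadrant (L is an assumption). A rating at nominal time T then falls T − L minutes after the latest needle.

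| L (min) | 15-minute rating | 60-minute rating |
|---|---|---|
| 5 | 10 | 55 |
| 10 | 5 | 50 |
| 15 | 0 | 45 |

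**6. Size of the noise.** Let a share p of subjects have a lower injection on one side only before a rating. Let it add x mm to a side that is random with respect to device, and let the paired SD be s.

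- The added term has mean 0 and variance p·x².
- Variance inflation: F = 1 + p·x²/s².
- Effective sample size: 30/F.
- 95% half-width: t(0.975, 29)·s·√F/√30, with t = 2.045.

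Only the 30 comes from the documents; p, x and s are assumptions.

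| p | x (mm) | s (mm) | F | Effective n | Half-width (mm) |
|---|---|---|---|---|---|
| 0 | – | 15 | 1 | 30 | 5.60 |
| 0.1 | 20 | 15 | 1 + 0.1·400/225 = 1.178 | 25.5 | 6.08 |
| 0.2 | 20 | 15 | 1 + 0.2·400/225 = 1.356 | 22.1 | 6.52 |
| 0.3 | 20 | 15 | 1 + 0.3·400/225 = 1.533 | 19.6 | 6.94 |
| 0 | – | 20 | 1 | 30 | 7.47 |
| 0.1 | 10 | 20 | 1 + 0.1·100/400 = 1.025 | 29.3 | 7.56 |
| 0.2 | 20 | 20 | 1 + 0.2·400/400 = 1.20 | 25.0 | 8.18 |
| 0.3 | 20 | 20 | 1 + 0.3·400/400 = 1.30 | 23.1 | 8.51 |

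**7. Power.** This was simulated for a Wilcoxon signed-rank test with 30 subjects, two-sided 0.05, normal differences, a true difference of 8 mm and SD 15 mm (6,000 runs per setting). Power is about 79% with no lower injections, 77% at p = 0.1 and x = 10, 67% at p = 0.2 and x = 20, and 62% at p = 0.3 and x = 20. The 8 mm is also an assumption.

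**The case for a change.** The best case for acting is that the omission is cheap to close now and hard to repair later. An injection time not written down on the day cannot be recovered reliably. The need for a lower injection is not randomized and can differ between sides. The ice rule shows that the authors knew this hour was sensitive. One consistent wording, one time field per side and a supportive analysis of ratings with no prior lower injection would cost little.

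Part of this stands: on the legible text, a lower injection can fall inside the rating hour. The rest does not carry a change, for four reasons.

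- The omission cannot be established. SAP 4.1 is blacked out, as is the text directly after the sequence sentence in SAP 4.1.3. Protocol 7.2.4 is redacted down to its title. There are further redactions after Protocol 7.2.3, after the rating text in 9.3.1.1 and just before the volume paragraph in 9.3.2.5. A timing rule, or a field for injection time, could be in any of these.
- Limiting the later ratings to the upper quadrant would change what is measured. Discomfort of the treated side as a whole would be lost, and subjects may find upper and lower pain hard to separate.
- The supportive analysis would select subjects on a decision made after randomization, within a sample of at most 30. It would correct no result shown to be wrong.
- The large effects come from the worst corner of the assumed range. Inclusion criterion 3 requires the same severity grade on both sides, which makes one-sided lower injections less likely. The model also lets the added pain persist undiminished from 15 to 60 minutes. The legible text ties no test or power target to these ratings.

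**Conclusion.** No change to the plan is called for. The observation is accurate as far as the text can be read: the later ratings are by side, are timed from that side's upper quadrant, and are not visibly shielded from a lower injection. But the area is stated consistently, the clock wordings agree once Protocol 9.3.1.1 is read, and one device per side makes a side-level score interpretable. Rating the side rather than the quadrant is a fair trade-off. Any rule on the timing of lower injections may lie under the redactions, so whether one exists is a question for those holding the full text.

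If lower injections do precede ratings, the cost is precision in non-primary measures. Under the assumed inputs, variance rises by about 3% to 53%, and the half-width grows by at most 1.34 mm (6.94 − 5.60) at SD 15 or 1.04 mm (8.51 − 7.47) at SD 20. The expected difference between devices does not shift, provided that the side needing a lower injection is unrelated to the device it received, which randomization and blinding support. The primary comparison is untouched.
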